9.4 Renal safety monitoring

9.4.1 Renal safety monitoring

Every renal laboratory trigger or renal event must be followed up by the investigator or designated personnel at the trial site. Recommended actions and follow-up assessments are listed in [Table 9-4](#) and [Table 9-5](#), respectively.

Table 9-4 Specific Renal Alert Criteria and Actions

Renal Event	Actions
Serum creatinine increase 25 – 49% compared to baseline	Confirm 25% increase after 24-48h Follow up within 2-5 days
Serum creatinine increase > 50 % compared to baseline	Confirm > 50 % within 24-48 hours after receipt of the abnormal value If confirmation of abnormal value is not possible in this timeframe study drug must be withheld until further evaluation is possible Consider drug interruption Consider patient hospitalization / specialized treatment
Albumin- or Protein-creatinine ratio increase \geq 2-fold compared to screening or baseline levels whichever is higher	Confirm value after 24-48h Perform urine microscopy Consider drug interruption / discontinuation
New onset dipstick proteinuria \geq 3+	
Protein-creatinine ratio (PCR) \geq 1000 mg/g or \geq 100 mg/mmol	
New onset dipstick glucosuria \geq 1+ not due to diabetes	Blood glucose (fasting) Perform serum creatinine, ACR
New onset dipstick hematuria not due to trauma	Urine sediment microscopy Perform serum creatinine, ACR

Additional specialized assessments are available to assess renal function or renal pathology. (Note: In exceptional cases when a nephrologist considers a renal biopsy, it is strongly recommended to make specimen slides available for evaluation by Novartis to potentially identify project-wide patterns of nephrotoxicity.)

Whenever a renal event is identified, a detailed patient history and examination are indicated to identify, document and potentially eliminate risk factors that may have initiated or contributed to the event:

- Blood pressure assessment (after 5 min rest, with an appropriate cuff size)
- Signs and symptoms such as fever, headache, shortness of breath, back or abdominal pain, dysuria, hematuria, dependent or periorbital edema
- Changes in blood pressure, body weight, fluid intake, voiding pattern, or urine output
- Concomitant events or procedures such as trauma, surgical procedures, cardiac or hepatic failure, contrast media or other known nephrotoxin administration, or other potential causes of renal dysfunction, e.g., dehydration, hemorrhage, tumor lysis

Table 9-5 Follow-up of renal events

Action	Follow up

Assess*, document and record in the Case Report Form (CRF) or via electronic data load. Review and record possible contributing factors to the renal event (co-medications, other co-morbid conditions) and additional diagnostic procedures (MRI etc) in the CRF.
	
 • Urine dipstick and sediment microscopy • Blood pressure and body weight • Serum creatinine, electrolytes (sodium, potassium, phosphate, calcium), bicarbonate and uric acid

Monitor patient regularly (frequency at investigator's discretion) until:
	
 • Urine output • Event resolution: (sCr within 10% of baseline or protein-creatinine ratio within 50% of baseline)
	
or

	
 • Event stabilization: sCr level with $\pm 10\%$ variability over last 6 months or protein-creatinine ratio stabilization at a new level with $\pm 50\%$ variability over last 6 months.

* Urine osmolality: in the absence of diuretics or chronic kidney disease this can be a very sensitive metric for integrated kidney function that requires excellent tubular function. A high urinary osmolality in the setting of an increase in sCr will point toward a "pre-renal" cause rather than tubular toxicity.

9.5 Reporting of study treatment errors including misuse/abuse

Medication errors are unintentional errors in the prescribing, dispensing, administration or monitoring of a medicine while under the control of a healthcare professional, patient or consumer (EMA definition).

Misuse refers to situations where the medicinal product is intentionally and inappropriately used not in accordance with the protocol.

Abuse corresponds to the persistent or sporadic, intentional excessive use of a medicinal product, which is accompanied by harmful physical or psychological effects.

All study treatment errors and uses outside of what is foreseen in the protocol will be collected in the dose administration record (DAR) CRF. Study treatment errors are only to be reported to Novartis Drug Safety and Epidemiology department if the treatment error is associated with an SAE.

All instances of misuse or abuse must be documented in the adverse event (AE) CRF irrespective of the misuse/abuse being associated with an AE/SAE. In addition, all instances of misuse or abuse must be reported to Novartis Drug Safety and Epidemiology. As such, instances of misuse or abuse are also to be reported using the SAE form/CRF. [Table 9-6](#) summarizes the reporting requirements.

Table 9-6 Summary of reporting requirements for medication errors

Treatment error type	Document in Dose Administration (DAR) CRF	Document in AE CRF	Complete SAE form/CRF
Unintentional study treatment error	Yes	Only if associated with an AE	Only if associated with an SAE
Misuse/Abuse	Yes	Yes	Yes, even if not associated with a SAE

9.6 Pregnancy reporting

To ensure patient safety, each pregnancy occurring after signing the informed consent must be **reported to Novartis within 24 hours** of learning of its occurrence. The pregnancy should be followed up to determine outcome, including spontaneous or voluntary termination, details of the birth, and the presence or absence of any birth defects, congenital abnormalities, or maternal and/or newborn complications.

Pregnancy must be recorded on the Pharmacovigilance Pregnancy Form and reported by the investigator to the local Novartis Drug Safety and Epidemiology Department. Pregnancy follow-up should be recorded on the same form and should include an assessment of the possible relationship to the study treatment.

Any SAE experienced during the pregnancy and unrelated to the pregnancy must be reported on a SAE form.

The study drug must be discontinued, though the patient may stay in the study, if she wishes to do so. All assessments that are considered as a risk during pregnancy must not be performed. The patient may continue all other protocol assessments.

Pregnancy outcomes should be collected for the female partners of any males who took study treatment in this study. Consent to report information regarding these pregnancy outcomes should be obtained from the mother.

9.7 Early phase safety monitoring

The Investigator will monitor adverse events in an ongoing manner and inform the Sponsor of any clinically relevant observations. Any required safety reviews will be made jointly between medically qualified personnel representing the Sponsor and Investigator. Such evaluations may occur verbally, but the outcome and key discussion points will be summarized in writing (email) and made available to both Sponsor and all Investigator(s). Criteria pertaining to stopping the study/treatment or adapting the study design are presented above.

When two or more clinical site(s) are participating in the clinical study, the Sponsor will advise the Investigator(s) at all sites in writing (email) (and by telephone if possible) of any new, clinically relevant safety information reported from another site during the conduct of the study in a timely manner.

9.8 AEs of special interest

9.8.1 Ketoacidosis

In rare cases, SGLT-2 inhibitors can lead to ketoacidosis. Therefore, investigators must pay close attention for any signs of ketoacidosis. Signs and symptoms of ketoacidosis may include deep and rapid breathing, nausea, vomiting, severe abdominal pain, confusion, unusual fatigue or sleepiness and coma. All signs and/or symptoms and results from relevant laboratory tests must be reported on the AE eCRF. If ketoacidosis is confirmed, the study treatment should be handled as per [Section 7.2](#) and appropriate measures must be taken to correct the acidosis and monitor glucose levels according to standard of care.

Every case of ketoacidosis must be reported to the Ketoacidosis adjudication committee and the ketoacidosis adjudication eCRF must be completed.

9.8.2 Hypoglycemia

Stopping rule for hypoglycemia:

Because hypoglycemia is a potential risk of LIK066 treatment, glucose levels will be measured when a subject experiences a clinically symptomatic hypoglycemia. If a confirmed glucose level is <56 mg/dL by repeated measurement, study treatment may be discontinued and the patient will be treated according to standard of care for hypoglycemia.

During the course of the study, if any patient experiences symptoms of hypoglycemia (shaking, nervousness, hunger, nausea, palpitations, dizziness, or confusion), they will be instructed to seek immediate medical evaluation and treatment.

Education and reporting of hypoglycemia:

Patients with T2DM, treated with antidiabetic medications, especially with sulphonyurea or insulin, may be at increased risk of hypoglycemia. The doses of antidiabetic medications should be adjusted in patients, who, according to the investigator, could be at a safety risk of developing severe hypoglycemia. Every patient (all diabetic patients) must be educated regarding hypoglycemic symptoms and treatment. This education should include general review of hypoglycemia and use of glucometer as follows:

- Explain of possible triggers of hypoglycemia (eg, strenuous exercise, delayed meals, changes in meal composition, illness, etc.).
- Explain the symptoms of hypoglycemia such as dizziness, lightheadedness; palpitations, heart racing/pounding, shaking; sweating, hunger, blurred vision, impairment of motor function, confusion.
- Review of appropriate treatment for hypoglycemic events (oral glucose intake).

Each patient will receive a home glucose monitor with all appropriate supplies. When a subject experiences symptoms of hypoglycemia, blood glucose should be measured. At any time when the subject experiences symptoms of hypoglycemia, the subject should treat the event as appropriate. Information related to the event should be recorded in the glycemia study diary as follows:

- The glucose value.
- Circumstances (strenuous exercise, delayed or missed meals, alcohol consumption etc.) under which the hypoglycemic event occurred.
- Time of occurrence in relation to the last medication and to the last meal intake.
- Time when the event starts and ends.
- Additionally, if a subject performs routine self-monitoring of blood glucose, any asymptomatic plasma glucose < 70 mg/dL (< 3.9 mM) should be treated and recorded in the glycemia study diary.

The subject must return the study diary at the next scheduled visit.

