6.6 Permitted dose adjustments and interruptions of study treatment

Investigational treatment dose adjustments and/or interruptions are not permitted.

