7.2 Discontinuation of study treatment

Discontinuation of study treatment for a patient occurs when study treatment is stopped earlier than the protocol planned duration. Discontinuation of study treatment can be decided by either the subject or the investigator.

Study treatment must be discontinued under the following circumstances:

- Patient decision - patients may choose to discontinue study treatment for any reason at any time.
- The investigator believes that continuation would negatively impact the safety of the patient or the risk/benefit ratio of trial participation.
- Any protocol deviation that results in a significant risk to the patient's safety
- Pregnancy (see [Section 8.6](#) (Safety) and [Section 9.6](#) (Pregnancy reporting))
- Discontinuation may be considered when patients have to be treated by prohibited medications on a case by case basis.

- Use of prohibited treatment as per recommendations in [Table 5-1](#)
- Hypersensitivity (CTCAE grade 2 or higher) reaction to LIK066 requiring intervention.
- Clinically significant diarrhea, suspected to be related to the study drug and not responsive to recommended management per SOM that may put the patient at risk (identified by investigator after consultation with the sponsor)
- Symptomatic orthostasis confirmed by repeated orthostatic blood pressure changes (more than a 20 mmHg drop in systolic or 10 mmHg drop in diastolic blood pressure and increase in heart rate >20 bpm (compared to sitting results) when blood pressure and pulse are taken after at least 3 minutes (standing)
- Clinically significant urinary tract or genitourinary infections, at the discretion of the investigator and consultation with the sponsor
- Clinically symptomatic hypoglycemia confirmed by repeated blood glucose levels (<56 mg/dL)
- Ketoacidosis (symptoms of ketoacidosis include nausea, vomiting, abdominal pain, unusual tiredness and trouble breathing) confirmed by blood pH and ketones.
- For ALT, AST, total bilirubin and/or alkaline phosphatase elevations mandating study treatment discontinuations, please refer to [Section 9.3](#) and [Table 9-1](#) and [Table 9-2](#) for further instructions and monitoring. Of note, ALT and AST are abnormal at baseline in this study. Thus only elevation to >2X of the baseline value will trigger events listed in [Section 9.3](#).
- Adverse events, abnormal laboratory values or abnormal test result that indicate a safety risk to the patient, in the opinion of the investigator

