9.8.3 Orthostatic hypotension

Because orthostatic hypotension is a potential risk of LIK066 treatment, orthostatic blood pressure readings will be recorded throughout the study as shown in the [Assessment schedule](#).

Any patient with clinically significant symptomatic orthostasis (more than 20 mmHg drop in systolic or 10 mmHg drop in diastolic blood pressure and increase in heart rate >20 bpm) will have the study treatment placed on hold. In addition, individuals with orthostasis will be treated with volume replacement according to standard of care (refer to [Section 7.2](#) (Discontinuation of study treatment)).

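### Protocol 9.8.2 makes stopping optional for confirmed symptomatic hypoglycemia below 56 mg/dL, where Protocol 7.2 makes it mandatory

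*Protocol*

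**What the plan says.** Protocol 7.2 (Discontinuation of study treatment) introduces its list with "Study treatment must be discontinued under the following circumstances". One item reads "Clinically symptomatic hypoglycemia confirmed by repeated blood glucose levels (<56 mg/dL", and nothing in that item leaves the decision to the investigator.

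Protocol 9.8.2 (Hypoglycemia) has a paragraph labelled as the stopping rule for hypoglycemia. It says that glucose is measured when a subject has clinically symptomatic hypoglycemia, and then: "If a confirmed glucose level is <56 mg/dL by repeated measurement, study treatment may be discontinued". The patient is to receive standard-of-care treatment. The section does not mention 7.2.

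The SAP does not deal with stopping for hypoglycemia in its readable text.

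**The concern.** The protocol gives two instructions of different force for one safety event. Staff dealing with a low glucose value will naturally turn to the section on hypoglycemia. There they find an option to stop and no sign that another section has already removed that option.

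The event is foreseeable. Protocol 3.6 names hypoglycemia as a risk of LIK066. One entry route requires type 2 diabetes with HbA1c from 6.5% to 10%. Table 5-2 permits insulin and sulfonylureas, and 9.8.2 itself says that these may raise the risk. The trial is multicenter and has no data monitoring committee (10.4), so consistent handling depends largely on the text.

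At stake are the safety of a patient kept on drug after a confirmed symptomatic low, and uniform application of a discontinuation rule. A site that relies in good faith on 9.8.2 would also commit a protocol deviation.

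**Working it through.** No arithmetic applies. The only number is the threshold, and it agrees. The check is a comparison of the two rules, followed by a search for text that reconciles them.

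**Step 1: are the triggers the same?**

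| Element | Protocol 7.2 | Protocol 9.8.2 |
|---|---|---|
| Symptoms | Required | Required |
| Glucose threshold | Below 56 mg/dL | Below 56 mg/dL |
| Confirmation | Repeat measurement | Repeat measurement |
| Action on study treatment | Must stop | May stop |
| Discretion stated | None in the item | Yes, through the word may |
| Reference to the other section | None | None |

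The triggers match in every element; only the action differs. The 70 mg/dL figure later in 9.8.2 concerns treating and recording asymptomatic values and is not a competing stopping threshold.

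**Step 2: which actions satisfy both sections?** Stopping satisfies both. Continuing satisfies 9.8.2 and breaches 7.2. The option that 9.8.2 appears to offer therefore cannot be used without a deviation.

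**Step 3: is the 7.2 list really mandatory for this item?** The list is mixed. Stopping for a patient who needs a prohibited medication is described there as something to consider case by case, and another item reads "Clinically significant urinary tract or genitourinary infections, at the discretion of the investigator and consultation with the sponsor". These items state their own discretion. The hypoglycemia item states none, so the lead-in applies to it in full.

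**Step 4: does any other text settle the matter?** Section 9.7 says "Criteria pertaining to stopping the study/treatment or adapting the study design are presented above". That leans towards 7.2, which comes earlier, but it names no section and sets no order of precedence. Section 9.8.2 then follows with its own stopping rule. By contrast, 9.8.1 does make the link: "If ketoacidosis is confirmed, the study treatment should be handled as per", followed by a reference to Section 7.2. No precedence rule was found elsewhere in the readable protocol.

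**The case against.** The strongest reply is that the sections can be followed together. The word may does not forbid stopping, 7.2 is the dedicated section on discontinuation, and under 12.2 investigators sign up to every instruction in the protocol. On that reading 7.2 governs and a careful site stops. This is right as far as it goes. It also means that 9.8.2 offers an option no site may use, which is the defect. That sites would in fact diverge is an inference; the documents do not state it.

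A second reply is that patients are protected in other ways. Section 9.8.2 says that antidiabetic doses should be adjusted where the investigator sees a risk of severe hypoglycemia. Section 7.2 separately requires a stop when the investigator judges that continuing would harm the patient, or that an adverse event or abnormal value signals a safety risk. The sponsor monitors safety unblinded throughout. All of this stands and limits the harm. These provisions still depend on judgment, whereas the 7.2 hypoglycemia item does not.

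A third reply is that the missing cross-reference is not unusual, since 9.8.4 on Fournier's gangrene has none either. That is correct. The fault is the clash between must and may; the missing pointer only makes it harder to notice.

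A fourth is that some text directly after the 7.2 list is redacted and the Site Operations Manual is not available, so a clarification could exist there. It could, but the two readable sentences would still disagree.

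**Conclusion.** The inconsistency is real and should be corrected. It is an internal inconsistency in a safety stopping rule, not a fault in the statistical analysis. For an affected patient the difference is between stopping study drug and staying on it. How many patients that would concern cannot be estimated, because the documents give no rate for the event. The conclusion assumes that the readable text of 7.2 and 9.8.2 is in force as written.

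Three stronger readings are tempting and are not supported.

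- A reader might infer from 6.6, "Investigational treatment dose adjustments and/or interruptions are not permitted", that a site which does not stop has to carry on with the full daily dose. But the protocol does not apply 6.6 literally. It provides for holds or interruptions after a positive urine pregnancy test (8.6.7), for liver findings (9.3 and Table 9-2), for a creatinine rise (Table 9-4) and for orthostasis (9.8.3). None of these names hypoglycemia, but together they rule out reading 6.6 as absolute.
- A reader might count the days left to Day 84 after a scheduled visit as a measure of extra exposure. Such a count does not measure harm, and it is not an upper bound. Patients have home glucose monitors, so an event can occur between visits or before the first one.
- A reader might infer bias in the ALT comparison or in adverse-event counts by arm. Nothing in the documents shows either.

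**What to change.** In Protocol 9.8.2, replace the permissive clause with: *study treatment must be discontinued (see Section 7.2)*. Section 9.8.1 is the model for the cross-reference. Section 9.8.3 is not: it refers to 7.2 but puts treatment on hold, where 7.2 requires discontinuation for confirmed symptomatic orthostasis, so it has a similar mismatch.

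If the sponsor does want investigator discretion, write it into the hypoglycemia item in 7.2, as the genitourinary infection item already does, and use the same words in 9.8.2.

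The first option costs one sentence; the second adds a matching edit to the 7.2 item. Neither needs new visits, tests, data fields or tables. The downside of the first option is that a patient whose low might have been resolved by reducing insulin or a sulfonylurea would also come off study drug. Section 7.2 already requires that, so the change adds no new restriction.

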9.8.3 Orthostatic hypotension

Because orthostatic hypotension is a potential risk of LIK066 treatment, orthostatic blood pressure readings will be recorded throughout the study as shown in the [Assessment schedule](#).

Any patient with clinically significant symptomatic orthostasis (more than 20 mmHg drop in systolic or 10 mmHg drop in diastolic blood pressure and increase in heart rate >20 bpm) will have the study treatment placed on hold. In addition, individuals with orthostasis will be treated with volume replacement according to standard of care (refer to [Section 7.2](#) (Discontinuation of study treatment)).

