8.1 Assessment schedule

Subjects should be seen for all visits/assessments as outlined in the assessment schedule or as close to the designated day/time as possible.

Missed or rescheduled visits should not lead to automatic discontinuation. Subjects who prematurely discontinue the study for any reason should be scheduled for a visit as soon as possible, at which time all of the assessments listed for the final visit will be performed. At this final visit, all dispensed investigational product should be reconciled, and the adverse event and concomitant medications recorded on the CRF.

Table 8-1 Assessment Schedule

Epoch	SCREENING	Baseline	Treatment											EOS ²	Follow up Phone call
Visit Name	Screening	Baseline	Treatment											EOS	
Visit Numbers ¹	1	101	201 ³	202 ³	203 ³	204 ³	205 ³	206					207 ³	399	
Days	-44 to -16	-15 to -1	1	7	14	28	42	56					84	112	142
Time (post-dose)	-	-	0h	-	-	-	0h	0h ³	1h	2h	4h	6h	0h	-	
Informed consent ⁴	X														

Commercially Confidential Information

Inclusion / Exclusion criteria	X	X													
Medical history/current medical conditions	X														
Demography	X														
Alcohol Test and Drug Screen	X	X													
Hepatitis and HIV Screen	X														
Pregnancy and assessments of fertility ⁶	X		X			X		X					X	X	
Physical Examination	X	X				X		X					X	X	
Body Temperature	X	X	X	X	X	X	X	X					X	X	
Body Height	X														
Body Weight	X	X	X	X	X	X	X	X					X	X	
Waist and hip circumference	X	X	X										X	X	
BMI	X	X	X	X	X	X	X	X					X	X	
waist:hip ratio	X	X	X										X	X	
Blood Pressure and Pulse Rate ⁷	X	X ⁸	X	X	X	X ⁸	X	X ⁸					X ⁸	X	
ECG evaluation	X	X											X	X	
Blood chemistry	X	X		X	X	X		X					X	X	

Epoch	SCREENING	Baseline	Treatment											EOS ²	Follow up Phone call
Visit Name	Screening	Baseline	Treatment											EOS	
Visit Numbers ¹	1	101	201 ³	202 ³	203 ³	204 ³	205 ³	206					207 ³	399	
Days	-44 to -16	-15 to -1	1	7	14	28	42	56					84	112	142
Time (post-dose)	-	-	0h	-	-	-	0h	0h ³	1h	2h	4h	6h	0h	-	

Commercially Confidential Information

Hematology	X	X		X	X	X		X					X	X	
Urinalysis	X	X			X	X		X					X	X	

Commercially Confidential Information

Coagulation Panel ¹⁰	X	X												X	
---------------------------------	---	---	--	--	--	--	--	--	--	--	--	--	--	---	--

Commercially Confidential Information

PK blood collection					X	X	X	X	X	X	X	X	X		
---------------------	--	--	--	--	---	---	---	---	---	---	---	---	---	--	--

Commercially Confidential Information

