Dose administration			X ¹⁴												
---------------------	--	--	-----------------	--	--	--	--	--	--	--	--	--	--	--	--

Commercially Confidential Information

MRI ¹⁶		X											X	X ¹⁷	
Comments	As required														
Concomitant therapies	X ¹⁸														
Study completion information														X	
Adverse Events	As required														X
Serious Adverse Events	As required														X

¹ Visit structure given for internal programming purpose only

² If a patient withdraws from the study, or if study medication is discontinued for any reason, the patient should be scheduled for a subsequent visit at which time all assessments at the EOS visit should be performed.

³ All assessments to be performed pre-dose

⁴ Informed consent must be provided by all patients before any screening procedures are performed. Commercially Confidential Information

Commercially Confidential Information

⁶ Serum pregnancy tests will be performed at Screening and end of study; urine tests may be used at other timepoints.

⁷ Blood pressure and pulse rate will be measured in a sitting position unless otherwise noted.

⁸ Measured in sitting and standing positions to assess orthostatic hypotension.

Commercially Confidential Information

¹⁰ Coagulation panel includes PT/INR and aPTT

Commercially Confidential Information

¹⁴ Patients will be provided with a supply of study medication to self administer once daily for 12 weeks (Day 2 to Day 84). Patients should bring all used and unused medications, and diaries, to each visit.

Commercially Confidential Information

¹⁶ MRI of abdomen and liver in all subjects. Quantification of liver fat will be performed on all subjects;

Commercially Confidential Information

¹⁷ Assessment is only to be performed at EOS if a patient withdraws from the study, or discontinues study treatment early for any reason.

¹⁸ A thorough review of any concomitant medications (including medication name, dose, unit, frequency, and route) should be performed at every visit.

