8.6.3 Blood chemistry

Albumin, alkaline phosphatase, total bilirubin, bicarbonate/CO₂, calcium, cholesterol, chloride, creatinine, CRP, γ GT, glucose, LDH, CPK, inorganic phosphorus, lipase, amylase, magnesium, potassium, total protein, AST, ALT, sodium, triglycerides, urea/BUN and uric acid. If the total bilirubin concentration is increased above 1.5 times the upper limit of normal, direct and indirect reacting bilirubin should be differentiated.

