8.6.6 Hematology

Hemoglobin, hematocrit, red blood cell count, white blood cell count with differential (e.g., neutrophils, basophils, eosinophils, monocytes, lymphocytes), erythrocyte sedimentation rate, and platelet count will be measured.

Coagulation parameters including aPTT, PT and INR will also be assessed; methods for assessment and recording are provided in the central laboratory manual.

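### No standing blood pressure reading is scheduled on drug before Day 28, although orthostatic hypotension is an adverse event of special interest; adding one at the existing Day 7 and Day 14 visits would cost little

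*Protocol*

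**What the plan says.** Protocol section 9.8.3, under the heading for adverse events of special interest, states that "orthostatic blood pressure readings will be recorded throughout the study as shown in the" Assessment schedule. The detail is therefore in Table 8-1 (section 8.1).

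- The row "Blood Pressure and Pulse Rate ⁷" has a mark at every visit from Screening to end of study.
- Footnote 7 sets the default: "Blood pressure and pulse rate will be measured in a sitting position unless otherwise noted".
- Footnote 8 marks the exceptions: "Measured in sitting and standing positions to assess orthostatic hypotension". It is attached to Baseline and Days 28, 56 and 84, and to no other visit.
- Footnote 3 covers Days 1, 7, 14, 28, 42 and 84 and the 0 h point on Day 56: "All assessments to be performed pre-dose".

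Protocol 11.5.2 and SAP 7.2 both plan to flag relevant orthostatic changes and to summarise vital signs by treatment and visit. Protocol 3.6 names volume depletion as the cause of the postural risk.

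**The concern.** The sponsor has singled out postural hypotension for special attention, yet the schedule has no standing measurement during the first four weeks of exposure. Day 1 does not fill the gap, because it is sitting only and before the first dose. Days 7 and 14 are sitting only.

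Two things follow. First, the planned orthostatic flags and by-visit summaries will have no standing data at Days 7 and 14. Second, a patient who stops drug before Day 28 contributes no standing reading on drug. Footnote 2 sends such a patient to an end-of-study assessment, and the blood pressure cell for that visit is sitting only as well.

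At stake is part of the safety and tolerability objective, which is secondary. The primary ALT endpoint and the capture of adverse events are unaffected.

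**Working it through.** The plan gives no figure to reproduce here. The check is a reading of Table 8-1, followed by counts.

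**Schedule, treatment period**

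| Day | Standing BP | Chemistry and hematology | Physical examination |
|---|---|---|---|
| 1 (pre-dose) | no | no | no |
| 7 | no | yes | no |
| 14 | no | yes | no |
| 28 | yes | yes | yes |
| 42 | no | no | no |
| 56 | yes | yes | yes |
| 84 | yes | yes | yes |

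**Visits after Day 1 with a standing reading.** There are six such visits (Days 7, 14, 28, 42, 56, 84). Now: 3/6. With Days 7 and 14 added: 5/6.

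**Opening stretch without a standing reading.** Now Days 1–27: 27/84 = 0.32. With the change, Days 1–6: 6/84 = 0.07.

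**Match with laboratory checks related to volume status.** Chemistry includes creatinine ("calcium, cholesterol, chloride, creatinine, CRP") and BUN ("triglycerides, urea/BUN and uric acid"). Hematology includes hematocrit ("Hemoglobin, hematocrit, red blood cell count, white blood cell count with differential"). Both panels are taken on treatment at five visits (Days 7, 14, 28, 56, 84). Those that also have a standing reading are 3/5 now and 5/5 with the change. These tests, with weight and sitting blood pressure and pulse, bear on volume status but do not measure postural change.

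**Added work.** Enrolment is 110, and at least 88 are expected to complete (Protocol section 4). Section 7.2 gives a minimum of 3 minutes standing.

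- All 110 attend both visits: 2 × 110 = 220 readings; 220 × 3 = 660 min = 11.0 h over the whole study.
- Only 88 attend: 2 × 88 = 176 readings; 176 × 3 = 528 min = 8.8 h.
- Per patient: 2 × 3 = 6 min.

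**Is there reason to look before Day 28?** The documents do not say when orthostatic events occur. They do show the drug acting early. Section 1.1 reports up to 3% placebo-adjusted weight loss over two weeks. Section 1.3.3 reports 2.39% and 2.38% after two weeks of 75 mg bid and 50 mg tid. Section 1.3.1 places GI events, mainly diarrhea, after single or multiple doses at 150 mg per day and above. The two-week weight figures in 1.3.3 come from other regimens and are not evidence of postural drops. They do show that the first two weeks are not an inactive period.

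**The case against.** The strongest reply is that this is a preference and not an error. Section 9.8.3 defers to the schedule, and the schedule delivers one pre-drug reading and three evenly spaced readings on drug. Those visits match the physical examinations from Baseline through Day 84. The opening gap of 27 days is no longer than the later ones: Days 29–55 and 57–83 are also 27 days each. The hold rule in 9.8.3 and the orthostasis stopping rule in 7.2 both require symptoms. Patients with symptoms are already covered, since adverse events are sought at each visit (9.1). Section 1.3.1 reports no orthostatic signal. No event rate supports the benefit, and 6 minutes counts standing time only.

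Much of this stands. There is no contradiction, the benefit is not quantified, and the extra recording and review work is real. Three points remain:

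- The opening gap differs from the later ones because no on-drug standing reading precedes it, and early stoppers never reach Day 28.
- Days 7 and 14 are better placed than Day 42, because the related laboratory tests are already taken there.
- Symptoms are not the only route to action. Section 7.2 also requires stopping for an abnormal test result that the investigator judges a safety risk, so a marked drop without symptoms could be acted on.

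**Conclusion.** The concern holds as a minor design improvement. Table 8-1 is unambiguous: no standing reading is scheduled on drug before Day 28, which leaves 27 of 84 treatment days (32%) uncovered at the start. Adding Days 7 and 14 reduces this to 6 of 84 (7%).

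The gain is earlier systematic detection and description of orthostatic change. No claim is made about how many events would be found. The workload figures assume that routine standing readings use the 3-minute minimum in section 7.2; the Site Operations Manual, which holds the measurement methods, was not available.

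**What to change.** Attach footnote 8 to the blood pressure and pulse cells for Days 7 and 14 in Table 8-1. Under footnote 3 the added readings would be pre-dose, like those at Days 28, 56 and 84. The wording of 9.8.3 and the hold and stopping rules can stay as they are.

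A patient who attends Day 7 on drug and stops between then and Day 27 would have at least one scheduled standing reading on drug. A patient who stops before Day 7 would gain nothing.

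The cost is two footnote markers and about 6 minutes of standing time per patient, at visits that already measure sitting blood pressure and pulse, plus the recording of the extra values and a few more flagged readings for sites to review. No new visit is needed. If the protocol is already in force, section 13.1 requires a written amendment, so the change is best included in the next one made for other reasons.
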